An unsigned copy of an IRB/IEC-and sponsor approved written ICF/assent must be prepared in accordance with ICH E6, Section 4, and all applicable local regulations (eg, Title 21 CFR Part 50 or EU Clinical Trials Directive 2001/20/EC) and provided to the sponsor. Each subject and the subject's parent(s) or legally acceptable representative must sign an approved informed consent/assent form before study participation. The form must be signed and dated by the appropriate parties. The original, signed and dated informed consent/assent form for each subject will be verified by the sponsor and kept in the investigator site file and a copy must be given to the subject

The subject or the subject's parent(s) or legally authorized representative should be informed in a timely manner if new information becomes available that may be relevant to the subject's willingness to continue participation in the study. The communication of this information should be documented.

When the subject reaches the age of 18 years while on study, and becomes competent to give informed consent, his/her consent will be obtained using separate ICFs to continue on the study.

With regard to the pharmacogenomic assessments described in [Section 9.5.1.4.2](#), an informed consent for collection of samples during the study for gene analysis will be prepared separately. Subjects may still be eligible to enroll in the study if they do not give informed consent for gene analysis.

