9.7.1.8.4 VITAL SIGNS

Descriptive statistics for vital signs parameters (ie, systolic and diastolic BP, pulse, respiratory rate, temperature, weight) and changes from baseline will be presented by visit. A shift table of hypertension from baseline to worst post-baseline grades will be provided.

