5.3.6.2 Summarization of Safety Data

Regarding summarization of mean and mean change from Baseline for laboratory, vital sign, and ECG data, if 2 or fewer subjects in each of the treatment groups have data for a given cycle, the applicable cycle(s) will not be summarized, and the table will be curtailed. For example, if at Cycle 10 the 3 treatment groups have 4, 3 and 1 subjects, respectively, then Cycle 10 will be summarized for all treatment groups. If at Cycle 11, the 3 treatment groups have 2, 2 and 1 subject, respectively, and at subsequent cycles no treatment has 3 or more subjects, then the table will not be produced for Cycle 11 and all subsequent cycles. However, for shift tables and other analyses of worst postbaseline values, all data will be included.

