5.6.3.4 Vital Signs

Vital signs will be summarized by assessment time and dose level for Phase 1 or study cohort for Phase 2 for the actual value and change from Baseline. Baseline will be defined as the last nonmissing result prior to the first administration of study drug.

Vital sign values will be evaluated on an individual basis by subject. Descriptive statistics for vital sign parameters (systolic [SBP] and diastolic [DBP] blood pressure (subjects $<$ 18 years old presented as percentile, other subjects \geq 18 years old presented in mmHg), heart rate, respiratory rate, body temperature, height, weight and BSA), as well as changes from Baseline, will be presented for each cycle and day.

Percentiles for height measurements will also be summarized using a shift table of lowest postbaseline from Baseline measurement by categories (5th, 10th, 25th, 50th, 75th, 90th, 95th).

Percentiles for BP values (only for subjects $<$ 18 years old [see Protocol Appendix 7 and 8]) will also be summarized using a shift table of worst postbaseline from Baseline measurement by categories ($<$ 90th percentile, 90th to 95th percentile, 95th to $<$ 99th percentile, SBP or DBP \geq 99th percentile). The overall percentile is taken as the worse of SBP/DBP percentiles.

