7 CHANGES IN THE PLANNED ANALYSES

There is no change from the planned analyses defined in protocol.

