8 DEFINITIONS AND CONVENTIONS FOR DATA HANDLING

8.1 Visit Windows

Visit windows will be defined to be upper and lower bounds of 1 day of the scheduled visit, following the protocol, which states that efforts should be made to conduct laboratory assessments and administer treatment on the day scheduled (± 1 day).

In Phase 1, tumor assessments for efficacy analysis are to be performed at Week 4 during Treatment Phase, and at Week 12, Week 24 and every 12 weeks thereafter or as clinically indicated in the Extension Phase. In Phase 2, tumor assessments for efficacy analysis are to be performed at Week 8 and Week 16 during Treatment Phase, and at Week 24 and every 12 weeks thereafter or as clinically indicated in the Extension Phase. All responses are to be confirmed at a follow-up examination after ≥ 28 days following the initial indication of response. Efforts should be made to conduct tumor assessments on the day scheduled (± 7 days).

In the calculation of descriptive statistics for laboratory values and vital signs, if a visit has multiple observations, the observation closest in date and time to the target visit day will be used in the analysis. If 2 or more observations have the same distance to the target visit day, the one that has the highest CTCAE grade or is farthest outside the normal range will be used. The purpose of this windowing is to provide a single record per subject per visit for the calculation of descriptive statistics and change from Baseline per visit. Other safety analyses (e.g., worst grade for laboratory results) will include all observations. All by-visit analyses will be performed using assessments at corresponding scheduled visits recorded in the eCRF. Data from all postbaseline assessments including those at scheduled and unscheduled visits will be used in the shift tables.

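### The SAP drops the protocol's all-ages hypertension shift table by grade, leaving subjects aged 18 to 21 with no shift table of measured blood pressure

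*SAP*

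**What the plan says.** Protocol 9.7.1.8.4 plans descriptive statistics for vital signs by visit and adds: "A shift table of hypertension from baseline to worst post-baseline grades will be provided". It gives no age restriction.

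SAP 5.6.3.4 plans descriptive statistics by cycle and day, with BP shown as a percentile for subjects under 18 and in mmHg for those 18 or over. It then specifies one BP shift table: "Percentiles for BP values (only for subjects" under "18 years old [see Protocol Appendix 7 and 8]) will also be summarized using a shift table of worst postbaseline from Baseline measurement". The categories are percentile bands with upper cuts at the 95th and 99th. No other BP shift table is described.

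SAP section 7 states: "There is no change from the planned analyses defined in protocol".

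Two general rules decide which readings reach which table. SAP 8.1 says of by-visit output: "All by-visit analyses will be performed using assessments at corresponding scheduled visits recorded in the eCRF". Of shift tables it says: "Data from all postbaseline assessments including those at scheduled and unscheduled visits will be used in the shift tables". SAP 5.3.6.2 drops cycles with very few subjects from the mean and mean-change tables, then adds: "However, for shift tables and other analyses of worst postbaseline values, all data will be included".

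Adults are expected. Protocol 9.3.1 admits subjects up to 21 years to Phase 2, and SAP 5.2.4 includes an 18-to-21 age group.

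**The concern.** The protocol names a safety output for all subjects. The SAP replaces it with a different one, restricts that by age, and declares no change.

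This matters because the SAP relies on shift tables to show worst values. A high BP reading taken between scheduled visits cannot enter a by-visit table. For a subject under 18 it enters the percentile shift table. For an adult it enters no BP table. Protocol 9.4.1.3 asks for closer BP monitoring in subjects who reach 160 systolic or 100 diastolic, so extra readings arise in the subjects of most interest.

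Hypertension is listed in SAP 5.6.2 as a clinically significant adverse event for lenvatinib, and Protocol 8.3 names it as a safety marker to be explored. At stake is one descriptive view of a known drug effect, missing for the older part of each Phase 2 cohort.

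**Working it through.** The plan states no figure to reproduce here. The check is a comparison of texts plus a count.

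**1. Planned table against specified table**

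| | Protocol 9.7.1.8.4 | SAP 5.6.3.4 |
|---|---|---|
| Scale | grade | percentile band |
| Population | no age limit | under 18 only |
| Comparison | baseline to worst post-baseline | baseline to worst post-baseline |

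Protocol 9.7.1.8.3, immediately before, uses the same shift construction for CTCAE grades of laboratory values, so I read grade here as CTCAE grade. The two tables then differ in scale as well as population. The grade table is absent at every age. Adults additionally have no substitute.

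**2. Where an adult reading goes.** Take an adult with 130/80 at baseline and at all scheduled visits, and one unscheduled reading of 160/100.
- By-visit mmHg statistics (SAP 5.6.3.4 with 8.1): the scheduled readings only.
- Sparse cycles (SAP 5.3.6.2): not shown at all.
- BP shift table (SAP 5.6.3.4): excluded by age.

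The 160/100 reading appears in no BP summary table.

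**3. How many subjects.** Protocol 9.3 allows at most 22 enrolled per cohort and 66 in Phase 2, with at least half of each cohort under 18 at consent.
- Per cohort: 22 − 0.5 × 22 = 11.
- Phase 2: 3 × 11 = 33 of 66.
- Among 10 subjects, where a cohort stops after Stage 1: 10 − 5 = 5.

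Phase 1 enrols only under 18, but Protocol 5.3 foresees crossings: "When the subject reaches the age of 18 years while on study". SAP 5.6.3.4 does not say whether age is taken at consent, baseline or measurement, and Protocol Appendices 7 and 8 end at age 17. The number who turn 18 on study is not given.

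**4. Can adults simply be added to the percentile table?** The adult limits in Protocol 9.4.1.2 and 9.4.1.3 are 140/90 for evaluating and starting treatment, and 160/100 beside the 99th percentile. Set these against the Appendix rows for age 17 at median height:

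| Reading | Age 17 limits (systolic 95th / 99th) | Category at 17 | Category at 18 (cuts 140/90, 160/100) |
|---|---|---|---|
| Girl, 138/85 | 129 / 136 | at or above 99th (highest) | below 140 and 90 (lowest) |
| Boy, 145/85 | 136 / 143 | at or above 99th (highest) | 140–159 (middle) |

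The same reading can fall two categories at a birthday. One pooled table would mix two scales that do not agree, so the adult table has to be separate.

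**The case against.** The strongest reply is that adult hypertension is well covered elsewhere. SAP 5.6.2 tabulates it as a clinically significant adverse event by CTCAE grade, with serious events and time to first onset, at all ages. SAP 5.2.5 summarizes antihypertensive use with no age limit. Protocol 9.4.1.3 calls for such treatment once 140 systolic or 90 diastolic is confirmed, so confirmed peaks should show up there. This stands. A reader might infer that adult hypertension goes unreported, and the documents do not support that. What these outputs lack is a comparison of measured BP at baseline with its worst later value.

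A reader might also infer that the protocol contradicts itself, because it sets three adult values beside the 95th percentile: 140/90, 150/90 and 150/95. They serve different actions: evaluating or treating, study entry, and restarting or ending closer monitoring. They can all be applied together. A choice among them arises only if someone builds an adult table on the 95th percentile. A table by grade need not use that boundary, and neither document prints the grade definitions for hypertension.

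Finally, the table shells are a separate document (SAP section 11) and were not available. They might contain an adult table. The SAP text, however, limits the table it describes to subjects under 18.

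**Conclusion.** The point holds and is minor. The SAP specifies no hypertension shift table by grade for any age, limits its only BP shift table to subjects under 18, and is wrong to declare no change from the protocol. Adults lose the shift from baseline to worst measured BP, including unscheduled readings. They do not lose hypertension events.

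The size is at most 11 of 22 per cohort by age at consent. It would be tempting to say that half of Phase 2 is affected. The figure of 33 of 66 requires every cohort to fill and to hold the maximum share of adults, and the documents give no expected number. It would also be wrong to say that under-18s receive the protocol's table: they receive a percentile table in its place. Nothing here bears on response rates, dose-limiting toxicity, eligibility or treatment rules.

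The conclusion assumes that grade in Protocol 9.7.1.8.4 means CTCAE grade and that the unseen shells follow the SAP text. If grade meant something else, the age restriction would still be an undeclared narrowing.

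**What to change.** In SAP 5.6.3.4, add the protocol's shift table by CTCAE v4.03 hypertension grade for all ages, using scheduled and unscheduled readings, and state how the grade is derived from measured BP.

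At minimum, add a separate shift table for subjects 18 or over in mmHg, also using all readings, with three categories:
- below 140 and below 90;
- 140–159 or 90–99, with neither value in the top range;
- 160 or more, or 100 or more.

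These cuts are already in Protocol 9.4.1.2 and 9.4.1.3. Keep the under-18 percentile table as it is and do not pool the two scales. Assign each subject to one table by age at baseline, or flag those who turn 18 on study. If the grade table is not produced, record that in SAP section 7.

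The cost is one more descriptive table and a few sentences, before database lock, from BP values already collected. Sites, visits, dosing and eligibility do not change.

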5.6.3.5 Electrocardiograms

Descriptive statistics for electrocardiogram parameters (HR, PR, QRS, QT, QTcB, QTcF and RR) and changes from Baseline will be presented by visit. ECG findings will be summarized. A shift table of worst postbaseline values from Baseline for ECG findings will be provided. A subject data listing will also be provided.

In addition, the number (percentage) of subjects with at least 1 postbaseline ECG result in QTc Bazett and QTc Fridericia during the treatment will be summarized. ECG results in QTc Bazett and QTc Fridericia will be categorized as follows:

- For subjects with Baseline and postbaseline data, maximum increase from Baseline (msec) of ≤ 30 , > 30 to ≤ 60 , and >60
- Maximum postbaseline value (msec) of ≤ 450 , > 450 to ≤ 480 , > 480 to ≤ 500 , and >500

5.6.4 Other Safety Analyses

Descriptive statistics and changes from baseline for left ventricular shortening fraction assessed on echocardiogram and LVEF assessed on echocardiogram or MUGA scans will be presented. Percent reduction from baseline will also be summarized.

Lansky play scores or Karnofsky performance scores (KPS) scores will be summarized by shifts from Baseline to worst postbaseline. A subject listing of Lansky play scores or KPS scores, will be provided.

In addition, Radiographic findings of proximal tibial growth plates and dental examination will also be summarized.

5.7 Other Analyses

5.8 Exploratory Analyses

See [Section 5.4.3](#) for Exploratory Efficacy Analyses.

6 INTERIM ANALYSES

For each disease cohort (Ewing sarcoma/pPNET, rhabdomyosarcoma and HGG) in Phase 2, there will be 1 futility analysis: this is planned for after the first 10 evaluable subjects have completed at least 4 treatment cycles and, if applicable, a confirmatory scan has been performed (in case of a PR or CR at week 16), or have discontinued study drug early (before Week 16). At the futility analysis, if there are no responders (CR/PR), then the enrollment for that cohort will be discontinued for lack of efficacy. If 1 or more responses are observed, the accrual will continue.

7 CHANGES IN THE PLANNED ANALYSES

There is no change from the planned analyses defined in protocol.

8 DEFINITIONS AND CONVENTIONS FOR DATA HANDLING

8.1 Visit Windows

Visit windows will be defined to be upper and lower bounds of 1 day of the scheduled visit, following the protocol, which states that efforts should be made to conduct laboratory assessments and administer treatment on the day scheduled (± 1 day).

In Phase 1, tumor assessments for efficacy analysis are to be performed at Week 4 during Treatment Phase, and at Week 12, Week 24 and every 12 weeks thereafter or as clinically indicated in the Extension Phase. In Phase 2, tumor assessments for efficacy analysis are to be performed at Week 8 and Week 16 during Treatment Phase, and at Week 24 and every 12 weeks thereafter or as clinically indicated in the Extension Phase. All responses are to be confirmed at a follow-up examination after ≥ 28 days following the initial indication of response. Efforts should be made to conduct tumor assessments on the day scheduled (± 7 days).

In the calculation of descriptive statistics for laboratory values and vital signs, if a visit has multiple observations, the observation closest in date and time to the target visit day will be used in the analysis. If 2 or more observations have the same distance to the target visit day, the one that has the highest CTCAE grade or is farthest outside the normal range will be used. The purpose of this windowing is to provide a single record per subject per visit for the calculation of descriptive statistics and change from Baseline per visit. Other safety analyses (e.g., worst grade for laboratory results) will include all observations. All by-visit analyses will be performed using assessments at corresponding scheduled visits recorded in the eCRF. Data from all postbaseline assessments including those at scheduled and unscheduled visits will be used in the shift tables.

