9.4.1.5 Management of Proteinuria

Regular assessment for proteinuria should be conducted as detailed in the Schedule of Assessments (Table 7 and Table 8). Guidelines for assessment and management of proteinuria are summarized as follows:

1. Grading according to CTCAE v4.03 will be based on the protein-creatinine ratio, and whenever possible, also on the 24-hour urinary protein result per investigator's

discretion. Management of study treatment administration will be based on the grade of proteinuria according to the Dose Modification Guidelines.

2. A spot protein-creatinine ratio test, and if possible a 24-hour urinary protein test as per investigator's discretion, to verify the grade of proteinuria is required in the following situations:
 - The first (initial) occurrence of $\geq 2+$ proteinuria on urine dipstick while on study treatment
 - A subsequent increase in severity of urine dipstick proteinuria occurring on the same lenvatinib/everolimus dose level
 - When there has been a lenvatinib/everolimus dose reduction and at the new dose level the urine protein dipstick result is 2+, 3+, or 4+
3. Urine dipstick testing for subjects with proteinuria $\geq 2+$ should be performed every 2 weeks (or on Day 1 and Day 15 or more frequently as clinically indicated) until the results have been 1+ or negative for 3 consecutive months.
4. In the event of nephrotic syndrome, lenvatinib must be discontinued.

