9.4.1.9 Management of Blood Glucose and Lipids

Hyperglycemia, hyperlipidemia and hypertriglyceridemia are recognized class effects of rapamycin derivatives, including everolimus. Glycemic and lipid control should be optimized before starting a subject on this study. Blood glucose will be monitored as specified in the Schedule of Procedures/Assessments. For subjects with blood glucose >ULN, a fasting (>6 hour, water only) blood glucose sample will be obtained. Grading will be based on the fasting blood glucose result. The choice of hypoglycemic agent should be individualized to the subject's clinical circumstances and follow standard medical practice.

Dose alterations of everolimus may be required in accordance with everolimus prescribing information, ie, Afinitor Disperz package insert or Votubia SmPC.

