9.4.1.12 Management of Hypocalcemia

Serum calcium should be monitored per the Schedule of Assessments. Corrected serum calcium should be used to assess the grade of hypocalcemia per CTCAE v 4.03, using the following formula:

$$\text{Corrected calcium} = ([4 - \text{serum albumin in g/dL}] \times 0.8 + \text{serum calcium})$$

The formula is not applicable when serum albumin concentration is normal (>4 g/dL); in such situations, the total (uncorrected) serum calcium should be used instead.

Hypocalcemia should be treated per institutional guidelines (eg, using appropriate calcium, magnesium, and Vitamin D supplementation) until resolution.

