9.5.1.5.3 LABORATORY MEASUREMENTS

Clinical laboratory tests to be performed, including hematology, chemistry, and urinalysis, are summarized in [Table 6](#). Subjects should be in a seated or supine position during blood collection. The Schedule of Assessments ([Table 7](#) and [Table 8](#)) shows the visits and time points at which blood for clinical laboratory tests and urine for urinalysis will be collected in the study.

Table 6 Clinical Laboratory Tests

Category	Parameters
Hematology	Hematocrit, hemoglobin, platelets, red blood cell count, and white blood cell count with differential (bands, basophils, eosinophils, lymphocytes, monocytes, neutrophils) International Normalized Ratio ^a
Chemistry	
Electrolytes	Bicarbonate, calcium, chloride, potassium, sodium, magnesium, phosphorus
Liver function tests	Alanine aminotransferase, alkaline phosphatase, aspartate aminotransferase, direct bilirubin ^b , total bilirubin
Renal function tests	Blood urea/blood urea nitrogen, creatinine
Thyroid function tests ^c	Thyroid stimulating hormone, free thyroxine (T4) level
Other chemistries	Albumin, amylase, calcium, glucose ^d , lactate dehydrogenase, lipase, total protein, triglycerides, cholesterol
Urinalysis for microscopy ^e	RBCs/high-power-field (HPF)
Urine dipstick testing ^e	Blood, protein, glucose
Other	Pregnancy test (serum or urine beta-human chorionic gonadotropin)

a: INR should only be performed as part of the screening assessment and when clinically indicated.

b: Direct bilirubin should be assessed if total bilirubin is elevated.

c: Thyroid function will be assessed every cycle

d: For subjects with blood glucose > ULN, a fasting (>6h, water only) blood glucose sample will be obtained.

e: If urine dipstick testing suggests a urinary tract infection, or if clinically indicated, a urine microscopy, culture, and sensitivity should be performed at the institution's laboratory. If urine protein is $\geq 2+$, then a spot test for protein-creatinine ratio and if possible, a 24-hour urine collection should be done to quantify the 24 hour urine protein excretion.

All clinical laboratory tests during the study will be performed by local laboratories. All hematology, blood chemistry (including pregnancy test, as applicable), and urinalysis samples are to be obtained prior to study drug administration and sent to the local laboratory on the day of collection, unless otherwise instructed.

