5.6.3.1 Hematology and Clinical Chemistry

Laboratory parameters will be reported using the following methods for hematology and clinical chemistry:

- Descriptive summary statistics for all major hematology and clinical parameters and their changes from Baseline will be calculated (n, mean, SD, median, Q1, Q3, min, max)
- Shifts from Baseline to worst postbaseline CTCAE grade (presented by each dose level in Phase 1 and overall, and each study cohort in Phase 2) for all clinical chemistry parameters and hematology parameters.

All hematology and clinical chemistry laboratory parameters will be listed by subject and visit.

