5.6.3.3 Urinalysis

The shift of Baseline to worst postbaseline proteinuria will be summarized. All urinalysis parameters (RBCs/high-power-field [HPF], blood, glucose, and protein [dipstick], 24-hour urine protein) will be provided by subject listing at each visit.

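### The SAP's worst-grade rule conflicts with the protocol's fasting-glucose grading, and the SAP omits the protocol's grading basis for calcium and proteinuria

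*SAP*

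**What the plan says.** **SAP.** Section 5.6.3.1 plans "Shifts from Baseline to worst postbaseline CTCAE grade" for all chemistry and hematology parameters. Section 8.1 reduces by-visit descriptive statistics to one record per visit, but leaves worst-grade laboratory analyses open to every observation. It adds that "Data from all postbaseline assessments including those at scheduled and unscheduled visits will be used in the shift tables". Section 5.6.3.3 says "The shift of Baseline to worst postbaseline proteinuria will be summarized" without naming a scale or a source test. The parameters it lists for the subject listing include dipstick protein and 24-hour protein, but not the protein-creatinine ratio. Section 5.6.3 puts CTCAE grades in the laboratory listings. Section 9 places derivation rules in separate documents.

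**Protocol.**
- Glucose: under Table 6 (9.5.1.5.3), a subject whose glucose exceeds ULN has a further sample taken: a fasting "blood glucose sample will be obtained". Section 9.4.1.9 then states: "Grading will be based on the fasting blood glucose result".
- Calcium: section 9.4.1.12 states: "Corrected serum calcium should be used to assess the grade of hypocalcemia per CTCAE v 4.03". It gives a formula and reverts to total calcium when albumin is above 4 g/dL.
- Proteinuria: under 9.4.1.5, grading "will be based on the protein-creatinine ratio" and, where possible, also on 24-hour urinary protein.

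**The concern.** The protocol says which measurement carries the grade for three laboratory toxicities, and the SAP repeats none of these rules. For glucose the SAP's wording also points the other way: a rule that takes the worst of all results will pick a non-fasting value whenever it grades higher than the fasting repeat.

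These three toxicities matter for this combination. SAP 5.6.2 lists hypocalcemia and proteinuria among the clinically significant adverse events for lenvatinib, and Protocol 9.4.1.9 names hyperglycemia as a class effect of everolimus. A shift table graded on a different basis from the one investigators were told to use could disagree with the adverse-event tables in the same report, and nothing in the report would explain the difference.

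**Working it through.** The plan states no figure on this point, so there is none to reproduce. The check sets the rules side by side and adds one calculation, for calcium.

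**Glucose.** Let R be a glucose above ULN that triggers a repeat, F the fasting repeat, and g(x) the grade, which does not fall as glucose rises.
- Protocol 9.4.1.9: grade = g(F).
- SAP 8.1 with 5.6.3.1: grade = max[g(R), g(F)].
- Since max[g(R), g(F)] ≥ g(F), the SAP grade for the pair is never below the protocol grade. It is above it whenever R falls in a higher grade than F.

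The documents give no paired glucose data and no grade cut-points, so the direction is known but the frequency is not.

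**Calcium.** Protocol 9.4.1.12: corrected calcium = (4 − albumin) × 0.8 + serum calcium. Inclusion criterion 8 allows albumin down to 2 g/dL at entry. The protocol gives no calcium unit; mg/dL is assumed. The example uses a total calcium of 7.5.

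| Albumin (g/dL) | Correction | Total 7.5 becomes |
|---|---|---|
| 4.0 | (4 − 4.0) × 0.8 = 0.0 | 7.5 |
| 3.5 | (4 − 3.5) × 0.8 = 0.4 | 7.9 |
| 3.0 | (4 − 3.0) × 0.8 = 0.8 | 8.3 |
| 2.5 | (4 − 2.5) × 0.8 = 1.2 | 8.7 |
| 2.0 | (4 − 2.0) × 0.8 = 1.6 | 9.1 |

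Uncorrected values are therefore too low by the middle column, which pushes hypocalcemia grade upward. Turning mg/dL into grades needs an assumed band width. With 1.0 mg/dL (range 0.5 to 1.5), the shift at albumin 3.5 is 0.4/1.0 = 0.4 of a band (0.3 to 0.8). At albumin 2.0 it is 1.6/1.0 = 1.6 bands (1.1 to 3.2).

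The SAP does not say that total calcium is graded. Table 6 lists both calcium and albumin, so the corrected value can be derived. However, the derived variables in SAP 8.3 include the Schwartz formula and no calcium correction.

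**Proteinuria.** The protocol grades on the ratio, with 24-hour protein as an addition where possible. The SAP leaves the scale of its shift unstated. The list in 5.6.3.3 describes the listing, not the shift table, and it includes one of the protocol's two measures. Neither the size nor the direction of any error can be worked out.

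**Reach.** Under Protocol 9.5.1.5.1 investigators assign the CTCAE grade of each adverse event, and SAP 5.6.2 builds its safety-event tables from those events. DLTs are determined during the study by the investigator and the medical monitor, with the steering committee as needed. None of these uses the SAP's laboratory grading, and neither does the response endpoint.

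**The case against.** A reader might infer that all three toxicities will certainly be misgraded, and that the laboratory tables will contradict the adverse-event grades and dose decisions. The documents do not support that reading, for four reasons.

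- On calcium and proteinuria the SAP is silent rather than contrary. SAP 9 defers derivations to specifications that are not available here, and SAP 7 declares no departure from the protocol's planned analyses. The protocol's own laboratory analysis section (9.7.1.8.3) also asks for CTCAE shift tables without restating the rules.
- The sentence quoted from SAP 8.1 is not a fault in itself. Unscheduled results have to be included, because fasting repeats and triggered ratio tests may arrive that way. It bears on glucose only, and only together with the all-observations rule in the same section.
- Dose decisions and adverse-event grades are made by investigators during the study, so these descriptive tables cannot alter them.
- A simple switch to fasting glucose and ratio alone would do harm. Both tests are triggered rather than scheduled for everyone. SAP 5.6.3 bases percentages on subjects with both a baseline and a relevant postbaseline result, so subjects never triggered would drop out.

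All four points stand. They reduce calcium and proteinuria to a missing specification and they shape the fix. They do not remove the glucose conflict, because there the SAP's own text gives the instruction.

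**Conclusion.** The point holds in limited form. For glucose, SAP 8.1 with 5.6.3.1 conflicts with Protocol 9.4.1.9, and the conflict can only raise the tabulated hyperglycemia grade. This assumes that both members of the pair are in the database and that the trigger draw was not itself fasting. For hypocalcemia and proteinuria, the SAP lacks the protocol's grading basis, so misgrading is possible unless the programming specifications supply it. If the calcium correction were omitted, the graded value would be 0.4 to 1.6 mg/dL too low for albumin from 3.5 down to 2.0 g/dL, with no error at 4 g/dL or above. How many subjects that would reclassify cannot be computed, because the documents give neither an albumin distribution nor calcium cut-points. The effect is confined to laboratory shift tables and graded listings. Adverse-event tables, DLT decisions and the primary endpoint are untouched. The change is worth making before the tables are programmed, but the trial's conclusions do not depend on it.

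**What to change.** **Glucose (SAP 5.6.3.1 and 8.1).** Exempt high glucose from the all-observations rule.
- Where a fasting repeat follows a value above ULN, grade on the fasting result.
- Treat subjects never above ULN as having no high-glucose grade, so that they stay in the denominator.
- Report values above ULN with no fasting repeat separately, as not graded on a fasting sample.

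**Calcium (SAP 5.6.3.1, with the formula in 8.3).** Grade hypocalcemia on the protocol's corrected calcium, and on total calcium where albumin is above 4 g/dL. State what is done when albumin is missing. Because SAP 5.6.3 reports in SI units, say that the correction is computed in the formula's own units first.

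**Proteinuria (SAP 5.6.3.3).** Define the shift for all subjects on dipstick protein, which is the scheduled measure. Add a summary of worst proteinuria grade by ratio (or 24-hour protein) among those tested, and count subjects never triggered as not requiring a ratio. Add the ratio to the listing.

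**Cost.** A short SAP revision and derivation code, with no protocol amendment. No new data are needed if the eCRF identifies fasting repeats and holds the ratio results; the documents do not show whether it does. If the programming specifications already contain these rules, the calcium and proteinuria items reduce to a cross-reference. The glucose wording in SAP 8.1 would still need correcting.
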